12.2. Objective Findings

Clinically significant abnormal objective findings (eg, clinical laboratory value, ECG value, and physical examination observation) will also be recorded as AEs.

When a clear diagnosis is available that explains the objective findings, this diagnosis will be recorded as the AE, and not the abnormal objective finding (eg, viral hepatitis will be recorded as the AE, not transaminase elevation). If a definite diagnosis is not available, then record the sign (eg, clinically significant elevation of transaminase levels) or symptom (eg, abdominal pain) as the AE.

Clinical laboratory test results will be reviewed by the Investigator. The Investigator must determine the clinical significance of all out of range values. Clinical laboratory tests with possibly drug related or clinically relevant abnormal values of uncertain causality may be repeated. Any abnormal values that persist should be followed at the discretion of the Investigator. The Investigator will document that he/she has reviewed laboratory tests (for paper reports: initial and date all pages; for electronic reports: document in electronic system or add separate comment to CRF).

Clinical Laboratory Tests Outside the Normal Range: Any value outside the normal range will be flagged for the attention of the Investigator or appropriate designee at the study center. The Investigator or appropriate designee will indicate whether or not the value is of clinical significance. If the result of any test (or repeat test, if done) from the samples taken during screening is indicated as clinically significant and is not covered by the inclusion criteria in **Section 8.1**, the subject will not be allowed into the study. Additional testing during the study may be done if medically indicated. If a clinically significant abnormality is found in the samples taken after dosing, during the study, and/or at the EOS/EDV Visit, this should be recorded as an AE and the subject will be followed until the test(s) has (have) normalised or stabilised.

All on-site ECG tracings will be reviewed by the Investigator. The Investigator must determine the clinical significance of all abnormal ECGs. ECG with possibly drug-related or clinically relevant abnormal findings of uncertain causality may be repeated. Any abnormal ECGs that persist should be followed at the discretion of the Investigator. ECG tracings will be initialed and dated on all pages by the Investigator.

12.3. Collection and Recording of Adverse Events

All pre-treatment events and AEs must be recorded in the subject's study records/source documents. All pre-treatment events must be recorded on the CRF. All AEs must be recorded on the CRF from first dose administration through the final study visit. All SAEs must be recorded on the CRF from the time informed consent/assent is obtained through the final study visit.

All AEs will be followed until resolution, stabilization of the condition, the event is otherwise explained, or the subject is lost to follow-up.

Each AE is to be evaluated for duration, severity, frequency, seriousness, action taken with the study treatment, outcome, and causal relationship to the study treatment. Definitions for severity, frequency, action taken with the study treatment, outcome, and causal relationship to the study treatment are presented below.

The severity of AE:

- **Mild** – Ordinarily transient symptoms that do not influence performance of subject's daily activities. Other treatment is not ordinarily indicated.
- **Moderate** – Marked symptoms sufficient to make the subject uncomfortable. Moderate influence on performance of subject's daily activities. Other treatment may be necessary.
- **Severe** – Symptoms cause considerable discomfort. Substantial influence on subject's daily activities. May be unable to continue the study, and other treatment may be necessary.

The frequency of AE:

- **Once** – an isolated episode.
- **Intermittent** – occurs on 2 or more separate occasions.
- **Continuous** – does not abate from date of onset to date of resolution.

The action taken with the study treatment:

- **Drug Interrupted** – Study drug stopped temporarily.
- **Drug Withdrawn** – Study drug stopped permanently.
- **Dose Reduced**.
- **Dose Increased**.
- **Dose Not Changed**.
- **Not Applicable**.
- **Unknown**.

The outcome of the AE:

- **Recovered/Resolved**.
- **Recovering/Resolving**.

- **Not Recovered/Not Resolved.**
- **Recovered/Resolved with Sequelae.**
- **Fatal.**
- **Unknown.**

The causal relationship of the AE to the study treatment:

- **Not related**
 - **Not related** – Improbable temporal relationship and is plausibly related to other drugs or underlying disease.
- **Related**
 - **Possible** – occurred in a reasonable time after study drug administration, but could be related to concurrent drugs or underlying disease.
 - **Probable** – occurred in a reasonable time after study drug administration, is unlikely to be attributable to concurrent drugs or underlying disease, and there is a plausible mechanism to implicate the study drug.
 - **Definite** – occurred in a reasonable time after study drug administration and cannot be explained by concurrent drugs or underlying disease. The adverse event should respond to dechallenge/rechallenge, however, this is not mandatory before assigning a definite causality.

The Medical Monitor is the initial contact person for protocol-related questions or discussion of AEs. The contact information for the Medical Monitor as well as other emergency contact information can be found in [Table 1](#) of this protocol.

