
Study Drug (Aptiom), Dosage and Mode of Administration:

The drug dosage form will be commercial tablets of 400 mg Aptiom (ESL) in 30 count bottles with an added supplemental study label. An Interactive Web/Voice Response System will be used to manage subject screening and enrollment.

Tablets will be taken by mouth, QD.

Aptiom may be taken with or without food. Tablets may be crushed and mixed with food if the subject is incapable of swallowing a tablet. All tablets must be taken simultaneously. Subjects are to take study drug at approximately the same time each day.

Duration of Treatment: 30 weeks**Reference Therapy, Dosage and Mode of Administration:** None**Concomitant Medications:**

The following medications are prohibited during the study. Subject may not have taken any medication prohibited for this protocol within 4 weeks prior to screening.

- OXC.
- Warfarin, felbamate, vigabatrin, and perampanel (unless at stable dose with safety testing for ≥ 1 year).
- Ezogabine.
- Other experimental/investigational drugs taken as part of a clinical trial.

The following drugs and treatments are allowed during the study:

- Vagus nerve stimulation.
- Steroids.
- Benzodiazepines at stable dose (as AEDs).
- Chronic medications (other than those prohibited, taken at a stable dose).
- Any other drug that, in the opinion of the Investigator is necessary for the medical treatment of the subject, provided it is not a prohibited medication.

See [Section 10.2](#) to [Section 10.4](#) of the full protocol for further discussion of concomitant medications.

Study Endpoints:

Primary Endpoint: The proportion of subjects completing 24 weeks adjunctive therapy during Maintenance Phase (Visit 9).

Efficacy Endpoints:

- Seizure data via the paper diary will be used to calculate the following seizure related endpoints:
 - Standard Seizure Frequency (SSF) during the first 12 weeks, the last 12 weeks, and the 24 weeks of the Maintenance Phase.
 - 50% and 75% responder rate (calculated as 50% and 75% reduction in SSF from baseline) as evaluated during the first 12 weeks, the last 12 weeks, and the 24 weeks of the Maintenance Phase.
 - Relative reduction (%) in SSF from baseline during the first 12 weeks, the last 12 weeks, and the 24 weeks of the Maintenance Phase.
 - Proportion of seizure-free subjects during the first 12 weeks, the last 12 weeks, and the

24 weeks of the Maintenance Phase.

- Time on ESL.

Other Endpoints:

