10. TREATMENT OF SUBJECTS

10.1. Study Drug

The drug dosage form will be commercial tablets of 400 mg Aptiom (ESL) in 30 count bottles with an added supplemental study label.

Tablets will be taken by mouth, QD.

Aptiom may be taken with or without food. Tablets may be crushed and mixed with food if the subject is incapable of swallowing a tablet. All tablets must be taken simultaneously. Subjects are to take study drug at approximately the same time each day.

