15.3.8. Safety Analyses

15.3.8.1. Adverse Events

All AEs will be coded using Medical Dictionary for Regulatory Activities (MedDRA) version 13.1 or higher. AEs are untoward medical occurrences:

- that occurred on or after the first dose of study medication.
- with a missing start date and a stop date on or after the first dose of study medication,
OR
- with both a missing start and stop date.

AEs will be summarized by MedDRA system organ class (SOC) and Preferred Term (PT).

The following AEs will be summarized and presented by MedDRA SOC and PT for the Safety population:

- All AEs (including number of events and subject incidence).
- AEs by severity (mild, moderate, severe).
- AEs by relationship to the study treatment (related, or not related).

The following conventions will be followed in summarizing AEs:

- For subject incidence summaries, each subject will be counted only once within each SOC and within each PT.
- If a subject reports more than one AE within a PT and/or a SOC, the AE with the highest known severity within each SOC and within each PT will be included in the summaries by severity.
- For summaries by relationship to the study medication, AEs will be grouped as “related” or “not related.” AEs assessed as “possible,” “probable,” or “definite,” will be grouped as “related.” If a subject reports more than one AE SOC and PT, and any are related, it will be summarized as related.

Summaries of SAEs, AEs leading to discontinuation or other AE summaries will also be provided if necessary. A listing of AEs, as well as a listing of deaths, SAEs, and AEs leading to discontinuation, will be presented.

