16.1.3. Relationship to Study Medication

Relationship, as indicated by the Investigator, is classed as “not related”, “possible”, “probable” (increasing severity of relationship) or “definite”.

For summaries by relationship to the study medication, AEs will be grouped as “related” or “not related.”

- AE Related: AEs with relationship to study medication assessed as “possible,” “probable,” or “definite”
- AE not Related: AEs with relationship to study medication assessed as “not related”
- AEs with a missing relationship to study medication will be regarded as related

If a subject report the same AE more than once within that SOC/ PT, the AE with the worst-case relationship to study medication will be used in the corresponding relationship summaries.

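### As defined, *Not related* needs both improbable timing and another drug or disease cause, so literal scoring biases the AE-by-relationship summary upward

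*Protocol*

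**What the plan says.** Protocol 12.3 splits causality into *Not related* and *Related*, and divides *Related* into three grades.

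- *Not related*: "Improbable temporal relationship and is plausibly related to other drugs or underlying disease".
- *Possible*: "occurred in a reasonable time after study drug administration, but could be related to concurrent drugs or underlying disease".
- *Probable*: reasonable timing, and the event "is unlikely to be attributable to concurrent drugs or underlying disease, and there is a plausible mechanism to implicate the study drug".
- The top grade, *Definite*: reasonable timing, and no other drug or disease can account for the event.

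For analysis, Protocol 15.3.8.1 states: "AEs assessed as “possible,” “probable,” or “definite,” will be grouped as “related". SAP 16.1.3 uses the same grouping, takes the investigator's assessment as recorded, uses the worst-case relationship when a subject repeats an event within a system organ class or preferred term, and adds: "AEs with a missing relationship to study medication will be regarded as related".

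On dosing, Protocol 10.1 says "Tablets will be taken by mouth, QD", and the synopsis gives "Duration of Treatment: 30 weeks".

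**The concern.** Causality has two parts here: whether the timing fits the drug, and whether something else explains the event. The *Not related* definition demands a particular answer to both. With daily dosing, most on-treatment events follow a recent dose, so the timing condition will often fail even when the investigator is sure that another drug or the disease is responsible.

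Such events should be common. Every subject takes at least one background AED (Protocol 8.1), and Protocol 12.1.1 asks for injuries and other consequences of seizures to be recorded as AEs.

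The trial has no control group and plans no comparison between arms. The relationship summary is therefore where a reader will look for event-level attribution to ESL. If some sites follow the wording and others follow clinical judgement, the pooled summary mixes two rules.

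**Working it through.** The plan gives no figure on this point, so the check is to set the four definitions against every combination of timing and cause and read off the analysis grouping. The definitions come from Protocol 12.3 and the grouping from Protocol 15.3.8.1 and SAP 16.1.3.

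| Timing | Other drug or disease cause | Category that fits as written | Analysed as |
|---|---|---|---|
| Reasonable | Clear | *Possible* only | Related |
| Reasonable | Could be | *Possible* only | Related |
| Reasonable | Unlikely or none; mechanism plausible | *Probable*, or *Definite* if nothing else can explain it | Related |
| Reasonable | None, but an external cause (accident) and no drug mechanism | None properly; the bare words come closest to *Definite* | Related if so scored |
| Improbable | Clear or could be | *Not related* | Not related |
| Improbable | None | None | Related if left blank |

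Three things follow.

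1. The first two rows get the same grade. An event clearly due to a background AED cannot be told apart from one where that AED is merely a candidate.
2. The external-cause row is a gap. *Not related* and *Possible* name only drugs and underlying disease, and *Probable* needs a mechanism pointing to the study drug.
3. *Not related* is reached only through improbable timing. Titration (2 weeks) plus maintenance (24 weeks) gives 2 + 24 = 26 weeks of daily dosing before any taper, so this route is narrow for on-treatment events.

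The documents give no AE rates, so size can only be illustrated. Let *r* be the share of subjects with at least one truly related AE, *u* the share whose AEs are all unrelated, and *m* the fraction of those scored *Possible* because of the wording. Then

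reported related incidence = *r* + *u* × *m*, and excess = *u* × *m*.

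All inputs are assumptions: *r* = 20% or 40%, *u* = 10% to 30%, *m* = 25% to 100%.

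- Smallest excess: 0.10 × 0.25 = 0.025, or 2.5 points.
- Largest excess: 0.30 × 1.00 = 0.30, or 30 points.
- *r* = 20%: reported 22.5% to 50%.
- *r* = 40%: reported 42.5% to 70%.
- *m* = 0 (nobody applies the wording literally): no excess.

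With about 50 subjects per arm (SAP 3.3), the excess is 50 × 0.025 = 1.25 to 50 × 0.30 = 15 subjects per arm.

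**The case against.** The best reply is that investigators do not use these definitions as an algorithm. The form first separates *Not related* from *Related*. Someone convinced of another cause would have to enter the *Related* branch to reach *Possible*, whose wording expresses uncertainty. Improbable timing is undefined and could be read as an onset or course that does not suit the drug. Some AEs arise off drug, because collection runs to Week 31 while any taper ends earlier. All of this stands as a reason why the problem may occur less often. None of it removes the stated rule, and the SAP does not correct it.

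Counting *Possible* and missing as related is a defensible, conservative safety convention. It errs towards over-attribution and so does not hide a signal. That also stands, and the grouping need not change. The blank-field route is probably minor, since Protocol 16.1 describes a system able to highlight required fields.

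The importance should not be exaggerated either. Related AEs are not a listed safety endpoint in Protocol 6.4 or SAP 2.4.4. Change from baseline in LAEP and in sodium gives before-and-after safety evidence that does not depend on this grading.

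A reader might infer that *Not related* is all but unusable and that the related-AE table will approach the all-AE table. The documents do not support that: it would need near-universal literal scoring, and they say nothing about how sites score. Nor can it be said that every unrelated AE falls into *Possible*; externally caused events do not fit there.

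**Conclusion.** The definition is defective. An on-treatment AE with reasonable timing that is clearly explained by a concurrent drug or underlying disease fits only *Possible*, and an externally caused AE fits no category properly. Because *Possible* and missing are analysed as related, literal use biases the AE-by-relationship summary upward, and uneven use makes sites inconsistent. The worst-case rule adds to this, since one such event is enough to move a subject's entry for that term.

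The direction follows from the text; the size does not. The range of 2.5 to 30 points rests wholly on assumed inputs and should not be cited as an estimate.

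The effect is confined to a descriptive breakdown. All-AE incidence, SAEs, discontinuations and the primary retention endpoint do not use the relationship grade. The wording deserves correcting, but it does not undermine the trial's main results.

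**What to change.** In Protocol 12.3, redefine *Not related* along these lines: *improbable temporal relationship, or clearly explained by other drugs, underlying disease or another cause*. Issue a site note saying that *Not related* takes precedence when the other explanation is clear, and that *Possible* is for events where it is only a candidate.

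Merely replacing the joining word with an or is not enough. A merely plausible other cause would then suffice for *Not related*, which overlaps with *Possible* and could under-count related events. Even the full rewording leaves one awkward combination: reasonable timing, another cause unlikely but not excluded, and no plausible mechanism. The site note should say how to grade it.

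If data collection is already complete, keep the related / not related grouping and add to SAP 16.1.3 a table showing not related, possible, probable, definite and missing separately, with a footnote on the definition. The SAP already lists the four grades, so this needs no new data, and it shows how much of the related total is only *Possible*.

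The cost is a small protocol revision needing Sponsor and IRB/IEC approval (Protocol 17.5), a site note, and one added table. A change made mid-study would put two definitions into one summary; the separate-grade table would make that more visible but would not remove it.

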12.4. Immediately Reportable Events

The following medical events must be immediately reported to the Sponsor:

- SAE.
- Pregnancy.

Emergency contact information can be found in Table 1.

12.4.1. Serious Adverse Event

If the Investigator or study center staff becomes aware of a SAE that occurs in a study subject after obtaining informed consent through 30 days following the last dose of the study medication, this must be reported immediately to the Sponsor whether considered related or unrelated to the study drug. SAEs must be recorded on the CRF and the data recorded should agree with that on the SAE form.

SAEs will be followed until resolution, loss to follow-up, stabilization of condition, or the event is otherwise explained.

In addition to the initial telephone notification, an initial SAE form as applicable must be completed and signed and sent via fax or email (see Table 1) to PPD Pharmacovigilance

(PPD-PVG) within 1 business day of the Investigator or study center staff becoming aware of the event. The SAE form must be signed by the Investigator or appropriate designee. PPD-PVG provides the SAE form used to report SAEs.

The Sponsor or designee will promptly notify all study centers and Investigators of a SAE that is determined to be expedited to the Regulatory Authorities in accordance with applicable law(s) and regulation(s). These SAEs must be promptly reported to the Institutional Review Board (IRB) or Independent Ethics Committee (IEC) by the Principal Investigator or the appropriate person at the study center if required per IRB/IEC guidelines.

If an SAE is reported after participation of the study, the Investigator or an authorized delegate should report SAEs “spontaneously” to PPD-PVG if considered at least possibly related to the study drug.

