7. INVESTIGATIONAL PLAN

7.1. Overall Study Design

This is a 31-week, multicenter, 2-arm, prospective, open-label, non-randomized, Phase 4 study of ESL as adjunctive therapy in adult subjects with a diagnosis of epilepsy with POS. Two groups of ESL-naïve subjects will be evaluated. The groups are defined as follows:

- Arm 1 (ESL as first add-on): This group will include subjects who have been maintained on a regimen consisting of a stable dose of LEV or LTG for at least 1 month (28 days) prior to screening and who have not used any adjunctive treatment.
- Arm 2 (ESL as later add-on): This group will include subjects who have been maintained on a regimen consisting of a stable dose of 1-2 AEDs (excluding oxcarbazepine [OXC]) for at least 1 month (28 days) prior to screening and who have used adjunctive treatment in the past.

The Arm 1 subjects will allow an assessment of the efficacy and safety of ESL in subjects who are early in the course of their disease and being treated with one of the most common first line AEDs. The subjects in Arm 2 are similar to the subject population in the Phase 3 adjunctive studies, treatment-resistant subjects who are later in the course of their disease. The inclusion of these subjects in the present study will provide an assessment of the efficacy and safety of ESL as a later adjunctive therapy in a real world clinical setting. In addition, this study will provide data from both Arm 1 and Arm 2 for several behavioral, mood-related, and QOL-related assessments that were not evaluated in the Phase 3 program.

Approximately 190 subjects will be enrolled (approximately 93 subjects in Arm 1 and 97 subjects in Arm 2).

The study will consist of a Screening Phase of 1 to 2 weeks, followed by a 2-week Titration Phase, a 24-week Maintenance Phase, and a Safety Follow-up/Taper Phase of 4 weeks. The last visit in the Maintenance Phase (Visit 9) is considered the End of Study (EOS) visit.

The screening visit should take place 7 - 10 days prior to the titration visit, and may be extended to 7 – 17 days if required with consent of medical monitor. Subjects of Asian ancestry who require HLA-B*1502 testing (eg, do not have prior test results) may have the screening visit 7 - 17 days prior to the titration visit.

Subjects who withdraw prior to the EOS visit should have an Early Discontinuation Visit (EDV) within 72 hours.

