10.1.1. Treatment with Study Drug

Eligible subjects will begin the 2-week Titration Phase on Day 1 (Week 1), during which they will initiate treatment with ESL 400 mg/day and remain on that dose for 1 week (Days 1 - 7). Subjects will titrate to ESL 800 mg/day the beginning of week 2 (Day 8) and will remain on that dose for 1 week up to the beginning of the maintenance phase. Subjects will maintain a minimum dose of 800 mg/day for the Maintenance Phase; however, during the Maintenance Phase, subjects may titrate in weekly increments of 400 mg/day as medically indicated at the discretion of the Investigator up to a maximum dose of 1200 mg/day (Canadian sites) or 1600 mg/day (US sites) (based on maximum local labelled dose).

During the 24-week Maintenance Phase, only one reduction to a minimum of 800 mg/day is permitted. Subjects requiring doses < 800 mg/day will be discontinued from the study.

Subjects who complete the 24-week Maintenance Phase may choose to continue treatment with commercial ESL. Subjects who chose not to continue treatment with ESL for any reason will be gradually tapered off drug unless abrupt discontinuation of the drug is required in response to an AE. The taper schedule is provided in Table 5.

Table 5: Taper of Study Drug

Dose (mg/day)	First Week	Second Week	Third Week
800	400	Stop	Stop
1200	800	400	Stop
1600	800	400	Stop

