11.5.10. End of Maintenance/End of Study: Visit 9 (Week 27 ± 3 days)

- Record concomitant medications.
- Perform physical and neurological examination.
- Obtain vital signs and body weight.
- Perform a 12-lead ECG.
- For females of childbearing potential, obtain blood for serum β -hCG.
- Obtain blood sample and urine sample for clinical laboratory testing (including thyroid panel).
- Record LAEP.
- Record AEs.

- Dispense study drug if needed for taper (Note: Subjects who elect to continue on commercially available drug will not be dispensed additional ESL at this visit. Subjects who elect to discontinue ESL will be provided sufficient ESL to accommodate the appropriate taper regimen.)
- Collect study drug.
- Record any ESL dose change since the last study visit.
- Record any AED dose change since the last study visit.
- Collect paper seizure diary
- Distribute paper seizure diary
- Review seizure diaries.
- Administer questionnaires (EQ-5D, CGI-I, PGI-C, QOLIE-31, POMS-SF, NDDI-E, MOAS, and eC-SSRS).
- Ensure return of watch and data collection device.

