11.5.11. Early Discontinuation Visit

Subjects who withdraw prior to the EOS visit should have an early discontinuation visit (EDV) within 72 hours. Every effort should be made for all subjects prematurely discontinuing the study drug, regardless of cause, to undergo final evaluation described below:

- Record concomitant medications.
- Perform physical and neurological examination.
- Obtain vital signs and body weight.
- Perform a 12-lead ECG.
- For females of childbearing potential, obtain blood for serum β -hCG.
- Obtain blood and urine sample for clinical laboratory testing (including thyroid panel).
- Record LAEP.
- Record AEs.
- Collect study drug.
- Record any AED dose change since the last study visit.
- Collect paper seizure diary
- Distribute paper seizure diary
- Review seizure diaries.
- Administer questionnaires (EQ-5D, CGI-I, PGI-C, QOLIE-31, POMS-SF, NDDI-E, MOAS, and eC-SSRS).
- Dispense study drug if needed for taper.
- Ensure return of watch and data collection device.

11.5.12. Follow-up Visit: Visit 10 or Telephone Call 3 (Week 31 ± 7 days)

- Record AEs.
- Record concomitant medications.
- Review paper seizure diary.

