12.4.2. Pregnancy

Pregnancies that occur from the time that informed consent is signed through 30 days following the last dose of the study medication will be collected and reported on the Pregnancy Event Form.

If a subject or a subject’s partner becomes pregnant during the course of the study, they will be instructed to report the pregnancy to the Investigator (see below). All female pregnant subjects will be instructed to commence discontinuation of the study medication. Further, the subject (or female partner of male subject) will be requested to return promptly/within 48 hours of the first notification of pregnancy to the study center and undergo a serum/urine pregnancy test, as confirmation of pregnancy. If positive, the female pregnant subject will no longer receive any additional study medication. All pregnancies, whether or not the subject received any additional study medication, will be followed until resolution (ie, termination [voluntary or spontaneous] or birth).

To report a pregnancy, the Pregnancy Event Form must be completed and sent via fax to PPD- PVG within 1 business day of the Investigator or study center staff becoming aware of the pregnancy. The Sponsor provides the Pregnancy Event Form.

Pregnancy itself is not regarded as an AE unless there is a suspicion that the study drug may have interfered with the effectiveness of a contraceptive medication or other AEs were detected.

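### For completers who taper, the Week 31 contact nominally comes 9 or 16 days before the 30-day SAE and pregnancy window closes; after a two-week taper no permitted date reaches it

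*Protocol*

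**What the plan says.** **Reporting window.** Protocol 12.4.1 requires immediate reporting of any SAE the site becomes aware of "after obtaining informed consent through 30 days following the last dose of the study medication", and says SAEs must be recorded on the CRF. Protocol 12.4.2 sets the same limit for pregnancies: "through 30 days following the last dose of the study medication will be collected and reported on the Pregnancy Event Form".

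**Recording period.** Protocol 12.3 sets a different limit: "All SAEs must be recorded on the CRF from the time informed consent/assent is obtained through the final study visit". Non-serious AEs are likewise recorded only up to the final visit.

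**Last contact.** Protocol 7.1 plans "a Safety Follow-up/Taper Phase of 4 weeks". Visit 9 is at Week 27 ± 3 days (11.5.10). The one later contact, Visit 10 or Telephone Call 3, is at Week 31 ± 7 days (11.5.12, Table 2). Its tasks are AEs, concomitant medications and diary review. The last scheduled pregnancy test is at Visit 9 or the early discontinuation visit (EDV), per Table 2.

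**Taper.** Protocol 10.1.1 states: "The taper schedule is provided in Table 5". That table gives one week of tapering from 800 mg/day and two weeks from 1200 or 1600 mg/day. Completers who stop ESL receive taper supply at Visit 9 (11.5.10). Early leavers also taper unless an AE calls for an abrupt stop (10.1.2), but no section times a follow-up contact from their EDV or last dose.

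**The concern.** The taper takes place inside the four-week follow-up phase, so it uses up part of that phase. The reporting window starts from the last dose, while the contact is fixed to a study week. The longer the taper, the sooner after the last dose the contact falls and the more of the 30 days lies beyond it.

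Safety and tolerability is a secondary objective (Protocol 5.2), and SAP 16.1.5 tabulates SAEs by arm. SAEs and pregnancies arising after the last contact but inside the stated window are not actively asked about. A site following 12.3 could also close SAE recording before the period that 12.4.1 covers has ended. The length of observation after the last dose then depends on the final dose and on how the subject left.

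**Working it through.** **Inputs**
- Visit 9: Week 27 ± 3 days (11.5.10).
- Last contact: Week 31 ± 7 days (11.5.12).
- Taper: 7 days from 800 mg/day; 14 days from 1200 or 1600 mg/day (Table 5), taken to start at Visit 9.
- Window: last dose + 30 days (12.4.1, 12.4.2).

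**The plan's own figure.** With day = (week − 1) × 7 + 1, Week 27 is Day 183 and Week 31 is Day 211. The difference is 28 days, which reproduces the stated four weeks.

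**End of the window, in days after Visit 9** (taper + 30)
- One-week taper: 7 + 30 = 37.
- Two-week taper: 14 + 30 = 44.
- No study-drug taper: 0 + 30 = 30.

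**Nominal shortfall** (window end − 28)
- One-week taper: 37 − 28 = 9 days.
- Two-week taper: 44 − 28 = 16 days.
- No taper: 30 − 28 = 2 days.

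**Shortfall over the permitted windows.** Visit 9 may fall on Days 180 to 186 and the contact on Days 204 to 218. The contact is therefore between 204 − 186 = 18 and 218 − 180 = 38 days after Visit 9.

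| Route | Window end | Shortfall at latest contact | Shortfall at earliest contact |
|---|---|---|---|
| One-week taper | 37 | 37 − 38 = −1 (covered) | 37 − 18 = 19 |
| Two-week taper | 44 | 44 − 38 = 6 | 44 − 18 = 26 |
| No taper | 30 | 30 − 38 = −8 (covered) | 30 − 18 = 12 |

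There are 7 × 15 = 105 combinations of Visit 9 day and contact day. The window is covered in 3 of them for the one-week taper: Visit 9 three days early with the contact six or seven days late, and Visit 9 two days early with the contact seven days late. It is covered in none for the two-week taper and in 42 without a taper.

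**Sensitivity**
- If the last taper dose is at Visit 9 + 6 or + 13, each taper shortfall drops by one day. The one-week taper is then covered in 6 of 105 combinations and the two-week taper still in none.
- If sites count ± 7 days from the actual Visit 9 (contact at day 21 to 35), the shortfalls are 37 − 35 = 2 to 37 − 21 = 16 days, and 44 − 35 = 9 to 44 − 21 = 23 days.

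**Time from last dose to contact.** Nominally this is 28 days without a taper, 28 − 7 = 21 after one week and 28 − 14 = 14 after two weeks.

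**Early leavers, reading Week 31 literally.** A subject who stops at Week 15 (Day 99) with a two-week taper has a window ending on Day 99 + 14 + 30 = 143, well before Days 204 to 218. A nominal Day 211 contact falls on or after the window end for any stop up to Day 211 − 44 = 167. A stop at Week 26 (Day 176) gives 176 + 44 = Day 220, just beyond the latest contact.

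**Text against text.** Section 12.3 ends SAE recording on the CRF at the final visit. Section 12.4.1 covers SAEs to 30 days after the last dose and requires them on the CRF. Whenever the final visit comes first, the two sections give different end dates.

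**The case against.** The strongest reply is that 12.4.1 is a duty triggered when the site becomes aware of an event. It does not promise to ask every subject about events up to day 30. Subjects are told to report pregnancies, unscheduled visits are allowed at any time (7.1), and 12.4.1 has a route for SAEs reported after participation. A reporting window that outlasts the last scheduled contact can work. This stands: reporting in the gap remains possible, and what is lost is active ascertainment. It does not settle the 12.3 conflict. The post-participation route also covers only events judged at least possibly related, so it is narrower than the main duty.

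The effect on the analysis is limited too. The primary endpoint is completion at Visit 9. The SAP plans no statistical tests, no comparison of arms and no separate post-treatment AE analysis.

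Some stronger readings are tempting but not supported:
- **That the contact always falls before the window closes.** The protocol does not express the contact as 28 ± 7 days after Visit 9. Its own windows let a few one-week-taper schedules reach the end. Completers who move to commercial ESL or stop abruptly can be covered within the permitted window.
- **That early leavers are uncovered in the same way, so that 40% of Arm 1 and 50% of Arm 2 are affected** (from the assumed 60% and 50% completion). That needs a contact four weeks after the EDV, which no section states. On the literal reading the contact falls after the window for most of them. It is late and relies on recall, but it is not short.
- **That non-serious worsening of seizures goes uncollected within the window.** The 30-day window covers only SAEs and pregnancies.

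**Conclusion.** The point holds for completers who taper. The nominal shortfall is 9 days after a one-week taper and 16 days after a two-week taper. The two-week case cannot be closed by any permitted pair of dates (6 to 26 days short); the one-week case can be, but only at the edges of the visit windows. This assumes that the taper starts at Visit 9 and follows Table 5, and that each visit window is counted from Day 1.

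Two defects do not depend on the calendar arithmetic. Sections 12.3 and 12.4.1 set different ends for SAE recording, and follow-up for early leavers is not tied to the EDV or the last dose. The documents do not say how many completers will taper, so the number of subjects affected cannot be given. The consequence is weaker and uneven ascertainment of late SAEs and pregnancies; the primary result is not affected.

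**What to change.** Reconcile Protocol 10.1.1 with Table 5, 11.5.12, 12.3, 12.4.1, 12.4.2 and Table 2. The last scheduled safety contact, the CRF recording period and the stated window after the last dose should agree, both for completers who taper and for early leavers. State explicitly how follow-up is timed for early leavers, and carry any change into the schedule in SAP 3.5. The taper and the choice of window are for the sponsor and are not questioned here.

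The cost is protocol wording. If the sponsor keeps the window and moves the contact, it would fall about one to three weeks later for subjects who taper. It may already be a telephone call, so no visit is added. The last-dose date needed to time it is already collected (Protocol 9.4).
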